## List of abbreviations

6MWT	6-minute-walk test
ABCA3	Human ATP-binding cassette transporter, sub-family A, member 3
AE	Adverse event
AMG	German drug law (Arzneimittelgesetz)
AR	Adverse reaction
BAL	Bronchoalveolar lavage
BB	Blood count
BP	Blood pressure
BSPAR	The British Society for Paediatric and Adolescent Rheumatology
BW	Body weight
chILD	Children's interstitial lung disease
CK	Creatine kinase
CO2	Carbon dioxide
CPI	Chronic pneumonitis of infancy
CQ	Chloroquine
Crea	Creatinine
CRF	Case report form
D	Day
DCF	Data clarification form
Diff	Differential blood count
DIP	Desquamative interstitial pneumonitis
DLCO	Diffusing capacity of the lung for carbon monoxide
DMC	Data monitoring committee
DMP	Data management plan
DPLD	Diffuse parenchymal lung disease
DZL	German Center of lung research
EC/IEC	Ethics committee/Independent ethics committee
ECG	Electrocardiogram
Echo	Echocardiography
ECLA	Extracorporeal lung assist
ECLS	Extracorporeal Life Support System
ECMO	Extracorporeal membrane oxygenation
e-CRF	Electronic case report form
EDC	Electronic data capture
EDTA	Ethylene diamine tetraacetic acid
EMEA	European Medicines Agency
FAF	Fundus autofluorescence
FDA	Food and Drug Administration
FEV1	Forced expiratory volume in 1 second
FiO2	Fraction of inspired oxygen
FVC	Forced vital capacity
GCP	Good clinical practice
GCP-V	GCP regulation
GFR	Glomerular filtration rate
gGT	Gamma-glutamic transferase
GIP	Giant cell interstitial pneumonitis
GLI	Global Lung function Initiative
GMCSF	Granulocyte macrophage colony-stimulating factor
GMCSF-Ra/b	Granulocyte macrophage colony-stimulating factor receptor subunit $\alpha$ and $\beta$
GOT	Glutamate oxaloacetate transaminase
GPT	Glutamate pyruvate transaminase
GvHD	Graft-versus-Host-Disease
HCQ	Hydroxychloroquine
HP	Hypersensitivity pneumonitis
ICH	International conference on harmonization of technical requirements for registration of pharmaceuticals for human use

---

[figure not shown]
[figure not shown]
IgG	Immunoglobulin G
IMP	Investigational medicinal product
ILD	Interstitial lung disease
IRB	Institutional review board
ISRCTN	International standard randomised controlled trial number
INN	International non-proprietary name
ISF	Investigator site file
ITT	Intention to treat
IZKS	Interdisciplinary centre for clinical trials
Lab	Laboratory
LDH	Lactatdehydrogenase
LIP	Lymphocytic interstitial pneumonia
LKP	Clinical Trial Director according (Leiter der Klinischen Prüfung)
MedDRA	Medical dictionary for regulatory activities terminology
MDAT	Medical database
MPAW	Mean airway pressure
NEHI	Neuroendocrine Hyperplasia of Infancy
Nkx2-1	NK2 homeobox 1 gene
NO	Nitrogen monoxide
NSIP	Nonspecific interstitial pneumonitis
PaO2	Partial pressure of oxygen in arterial blood
PcapO2	Partial pressure of oxygen in capillary blood
PAP	Pulmonary alveolar proteinosis
pCO2	Carbon dioxide partial pressure
pO2	Oxygen partial pressure
O2	Oxygen
O2-sat	Oxygen saturation
OCT	Ocular coherence tomography
O.I.	Oxygenation index
PEEP	Positive endexpiratory pressure
PIP	Positive inspiratory pressure
p.o.	Orally
PP	Per protocol
QOL	Quality of life
QC	Quality control
QT	QT-intervall in the ECG
RDS	Respiratory distress syndrome
RR	Respiratory rate
SAE	Serious adverse event
SAP	Statistical analysis plan
SAR	Serious adverse reaction
SAS	Statistical analysis system
SDV	Source data verification
SFTPB	Surfactant protein B
SFTPC	Surfactant protein C
SmPC	Summary of product characteristics
SOP	Standard operating procedure
SPSS	Statistics program
SSL	Secure Sockets Layer
SUSAR	Suspected unexpected serious adverse reaction
Temp	Body temperature
Ti	Inspiration Time
TMF	Trial master file
TTF1	Thyroid Transcription Factor-1
UIP	Usual interstitial pneumonitis
VA	veno-arterial
VV	veno-venous

[figure not shown]
## Overview Study plan HCQ

This randomized controlled study is embedded into the European Management Platform for Children's Interstitial Lung Diseases (chILD). Patients included into this register and biobank are eligible for inclusion into the trials (see 3.5.1).

The study contains two different study blocks:

[figure not shown]
[figure not shown]
Typical examples for the indication of these blocks:

If a patient already had been treated with HCQ longer than 3 months ago, it makes sense to include him/her into the START-HCQ block for several reasons among others, especially for :

- It is not obvious, if there was an effect of the HCQ treatment or not
- It is unclear which dose of HCQ was given or if the patient was compliant
- There are new aspects of the course of the patient's disease
- The child has become substantially (e.g. > 1 year) older

These blocks can be initiated in sequence as needed by the subjects. Each patient can participate in **each block only once**:

## Synopsis

Title	Hydroxychloroquine in pediatric ILD. START randomized controlled in parallel-group, then switch placebo to active drug, and STOP randomized controlled in parallel-group to evaluate the efficacy and safety of hydroxychloroquine (HCQ)
Short title	HCQ in pediatric ILD
EudraCT	2013-003714-40
IZKS trial code	2013-006
Indication	Diagnosed children's interstitial lung disease (chILD) in children and adults
Phase	2a
Treatments	
Test product: Hydroxychloroquine Sulfate (HCQ), one daily dose in the evening.
 
Reference therapy: Placebo
 
The treatments are organized in START and STOP blocks, which can be initiated in sequence, as needed by the subjects.

	START HCQ block
Block specific inclusion criterion (others see 3.6.1)	All subjects not currently on HCQ (last dose $\geq$ 3 months ago) and intention to widen treatment.
Primary objective	To evaluate the efficacy of HCQ after 28 days of treatment in chILD compared to placebo
Secondary objectives	
To evaluate the efficacy of HCQ after 56 days of treatment in chILD compared to 28 days
 
To evaluate the safety of HCQ after 28 and 56 days of treatment in chILD
 
To evaluate blood levels of HCQ after 28 and 56 days of treatment in chILD

Trial design	
Double blinded treatment
 
This is an exploratory Phase 2a, randomized, double-blind, placebo-controlled, parallel-group study and switched placebo to active drug, multicentre, multinational study in subjects with chILD genetically, histologically or clinically diagnosed.
 
This study includes:
 
 
• Screening Period (Day -28 through Day -3)
 
• Treatment Period (Day 1 through Day 56)
 

	STOP HCQ block
Block specific inclusion criterion (others see 3.6.1)	All subjects on chronic (> 3 months) treatment with HCQ (usually 6-10 mg/kg/d or individually tolerated dose) and intention to reduce treatment.
Primary objective	To evaluate the efficacy of HCQ after 84 days of treatment in chILD compared to placebo
Secondary objectives	To evaluate the efficacy of chronic (> 3 months) HCQ treatment in chILD compared to placebo To evaluate the safety of HCQ after > 3 months of treatment in chILD To evaluate blood levels of HCQ before and after treatment in chILD
Trial design	
Stop HCQ block
 
Open label treatment      Double blind treatment      Open observation
 
> 3 month      3 months      3 months
 
Stable baseline for -30 to -10 days
 
HCQ individual dose
 
no major changes in respiratory status or medication
 
Randomized withdrawal
 
placebo
 
No medication

This is an exploratory Phase 2a, randomized, double-blind, placebo-controlled, parallel-group, multinational withdrawal study in subjects with chILD and treated with hydroxychloroquine.

This study includes:

- History of Open Treatment Period (total of at least 3 months of continuing HCQ treatment until randomization)
- Screening Period (Day -30 through Day -10)
- Treatment Period (Day 1 through Day 84)
- Open observation period (Day 85 through Day 168)

Trial population	In addition to the block specific inclusion criterion the inclusion criteria are: See 3.6.1 in the protocol Allowed previous medication: see 4.1.10
	exclusion criteria: See 3.6.2
Trial duration	Until 2024/2025
Number of subjects	It is planned to enrol at least 80 subjects
Number of sites	Up to 100 trial sites are planned to participate
Primary outcome	START HCQ block Relative change trial day 1 (i.e. Visit 2) through day 28 (i.e. Visit 3) and relative change day 28 to day 56 (i.e. Visit 4) active compared to change placebo STOP HCQ block Relative change day 1 (i.e. Visit 2) through day 84 (i.e. Visit 5): change active compound compared to change placebo Oxygenation (see Table 3.3-1)
Secondary outcome	See 3.4
Statistical analysis	START HCQ block and STOP HCQ block The variable assessing the primary outcome is the response rate measured by the oxygen saturation in room air. Both blocks separately a) A difference between the changes in placebo and active phases is considered significant, if the oxygen saturation increases by $\geq 5\%$ . b) Patients are defined as responder if the oxygen saturation is increased by 5% compared to baseline. The numbers of responders are counted and compared by Fisher exact test. Both blocks together c) oxygen saturation and the correspondent responder will be analysed by a linear mixed model (or logistic regression respectively). If indicated, a Bayesian approach will be employed. If appropriate, the analyses will be adjusted for the stratification factor of the randomization: age group.

## Trial schedule

### START HCQ block

Table 1-1

Visit	Screening evaluations and Visit 1	Visit 2	Email-/Phone-Visit	Visit 3	Email-/Phone-Visit	Visit 4
Action	„Start of baseline“	“End of baseline“ + Day 1 of treatment	Every 7 days at home	End of 1 st Tx period	Every 7 days at home	“End of trial”
Trial day	-28 to -3	1	7, 14, 21 (+/- 3)	28 (-4, +7)	35, 42, 49 (+/- 3)	56 (-4, +7)
Demographics (e.g. sex, age)	X					
Patient information, informed consent	X					
Previous (last 12 months) and concomitant diseases	X	X	X	X	X	X
Previous (last 3 months) and concomitant treatments	X	X	X	X	X	X
Inclusion/exclusion criteria	X	X 				
Pregnancy test K	X*			X		X
Randomization a	X					
Trial medication supply to patient		X		X		
History (cardiotoxicity, hypoglycaemia)	X	X		X		X
Physical examination	X	X		X		X
Vital signs (BP, pulse, temp) b	X	X		X		X
ECG i	X*			X		X
Ophthalmologic review j	X*					X
Lab c (GOT/GPT/Crea/Potassium/CK/gGT/LDH/BB/DIFF / HCQ drug level, blood glucose)	X*			X		X
pO 2 , pCO 2 (capillary)	X	X 		X 		X 
O 2 -sat e , in room air	X	X	X	X	X	X
Respiratory rate, in room air	X	X	X	X	X	X
Retractions	X	X	X	X	X	X
Coughing	X	X	X	X	X	X
Oxygen demand	X	X	X	X	X	X
Chest x-ray	X 			X 		

CONFIDENTIAL

Visit	Screening evaluations and Visit 1	Visit 2	Email-/Phone-Visit	Visit 3	Email-/Phone-Visit	Visit 4
Pulmonary hypertension (Echo) j	X*					
Quality-of-life i	X*			X		X
Health Economics h	X*			X		X
Weight for height b	X*	X		X		X
Clinical course of lung disease	X 	X 	X 	X 	X 	X 
Exacerbation o	X 	X 	X 	X 	X 	X 
Adverse events	X	X	X	X	X	X
Drug accountability				X		X
Additionally in children > 5 years						
Spirometry / Bodyplethysmography a	X	X		X		X
6 minute walking distance (meter) g	X	X		X		X
O 2 -saturation before and after 6MWT	X	X		X		X
Borg scale t	X	X		X		X
Additionally in ventilated patients m						
Oxygenation index (OI) n	X	X	X	X	X	X
Duration (h) of mechanical ventilation	X	X	X	X	X	X
NO (%), ECLS (VV/VA/ECLA/Flow/time since insertion)	X	X	X	X	X	X

X\* Tests must be done before first drug dosing

X Test can be done according to the opinion of the treating physician

X Puncture site should be warm and well perfusedp.

X Chest x-ray is recommended if clinically indicated e.g. to answer the question if the disease is stable

X Re-check inclusion criteria 1

X (since last visit): Healthy / Sick-better / Sick-same / Sick-worse / Patient died

X Pulmonary exacerbation is defined as sustained worsening of the patient's condition from stable state and beyond normal day to day variations. The exacerbation is rated as indicated belowo.

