## STOP HCQ block

Table 1-2

Visit	Visit 1 + Screening	Visit 2	Email- /Phone- Visit	Visit 3	Email-/ Phone- Visit	Visit 4	Email-/ Phone- Visit	Visit 5	Email-/ Phone- Visit	Visit 6	Email- /Phone- Visit	Visit 7	Email- /Phone- Visit	Visit 8
Action	„Begin of baseline“	“End of baseline“ + Day 1 of withdrawal treatment	2 weeks of withdrawal, at home	4 weeks of withdrawal treatment	6 weeks of withdrawal, at home	8 weeks of withdrawal treatment	10 weeks of withdrawal, at home	“End of trial“ after 12 weeks of withdrawal treatment	2 weeks of open observation at home	Follow up after 4 weeks of open observation	6 weeks of withdrawal, at home	Follow up after 8 weeks of open observation	10 weeks of withdrawal, at home	Follow up after 12 weeks of open observation
Trial day	-30 to -10	1	14 (-7, +7)	28 (-7, +7)	42 (-7, +7)	56 (-7, +7)	70 (-7, +7)	84 (-7, +7)	98 (-7, +7)	112 (-7, +7)	126 (-7, +7)	140 (-7, +7)	154 (-7, +7)	168 (-7, +7)
Demographics (e.g. sex, age)	X													
Patient information, informed consent	X													
Previous (last 12 months) and concomitant diseases	X	X	X	X	X	X	X	X	X	X	X	X	X	X
Previous (last 3 months) and concomitant treatments	X	X	X	X	X	X	X	X	X	X	X	X	X	X
Inclusion/exclusion criteria	X	X 												
Pregnancy test k	X*			X		X		X						
Randomization a	X													
Trial medication supply to patient		X		X		X								
History (cardiotoxicity, hypoglycaemia)	X	X		X		X		X		X		X		X
Physical examination	X	X		X		X		X		X		X		X
Vital signs (BP, pulse, temp) b	X	X		X		X		X		X		X		X
ECG j	X*							X						X
Ophthalmologic review l	X*													X 
Lab c (GOT/GPT/Crea/Potassium/CK/gGT/LDH/BB/DIF F / HCQ drug level, blood glucose)	X*			X		X		X		X (only HCQ drug level)		X (only HCQ drug level)		X (only HCQ drug level)
pO 2 , pCO 2 (capillary)	X	X 		X 		X 		X 		X 		X 		X 
O 2 -sat e , in room air	X	X	X	X	X	X	X	X	X	X	X	X	X	X
Respiratory rate, in room air	X	X	X	X	X	X	X	X	X	X	X	X	X	X

CONFIDENTIAL

Visit	Visit 1 + Screening	Visit 2	Email- /Phone- Visit	Visit 3	Email-/ Phone- Visit	Visit 4	Email-/ Phone- Visit	Visit 5	Email-/ Phone- Visit	Visit 6	Email- /Phone- Visit	Visit 7	Email- /Phone- Visit	Visit 8
Retractions	X	X	X	X	X	X	X	X	X	X	X	X	X	X
Coughing	X	X	X	X	X	X	X	X	X	X	X	X	X	X
Oxygen demand c	X	X	X	X	X	X	X	X	X	X	X	X	X	X

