a Randomization must occur for logistic reasons as soon as possible after concluding all screening investigations and including the patient into the study. This secures delivery of the study medication in time to any study center.

b Weight (kg) and height (cm) will be measured with shoes and clothes off. Vital signs will be collected after the patient has been at rest for 5 minutes.

c Blood sample should include: Blood count with differential, GOT, GPT, gGT, Creatinine, LDH, Potassium, Creatine kinase, blood glucose. HCQ drug level (2 ml EDTA blood and 2 ml of Serum blood). Labor Manual will be provided.

d Spirometry / Bodyplethysmography will be performed pre-bronchodilator in children age  $\geq$  5 years. (If a child  $\leq$  5 years is already able to perform the listed investigations (spirometry or bodyplethysmography), these should also be performed and documented at the discretion of the investigator) The following lung function parameters will be assessed: FEV1 % predicted (recorded in L), FEV 1 (L), FVC % predicted (recorded in L), FVC (L); MEF 75 (L/s); MEF 50 (L/s); MEF 25 (L/s); TLC (L); ITGV (L); RV (L); R eff (kPa\*s/L); R eff predicted (%). SOP will be provided.

e Measurement of O2-Saturation, respiratory rate and O2 flow (if necessary) in awake patient at rest:

If not on O2: after 5 min at rest, room air, then measure twice over 1 min. each; the measurements have to be at least 1 min. apart; report the stable average value

If on O2:

- BEFORE withdrawal (after 5 min at rest with steady state O2 supplement, measure over 1 minute)
- Then withdraw O2 to obtain steady state O2-Sat. in room air (at least 30 seconds without change). Then measure twice over 1 min. each; the measurements have to be at least 1 min. apart; report the stable average value. If the O2-Sat falls below SpO2<80% place back in oxygen and note as exact value.

Document the time of measurement and state of the patient, usually "awake, at rest". Note: In babies avoid crying, eating, sleeping during measurement. Note: try to schedule patients at similar time of the day.

f Borg-Scale: assessment of dyspnea (0 – 10: 0 = no dyspnea at all, 5 = severe dyspnea, 10 = extremely severe dyspnea)

g Standard exercise testing (6-minute-walk test): SOP will be provided

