h Health economics assessment with the use of a special questionnaire which has to be filled out by the parents or adult patients.

i Quality of Life assessment with the use of the questionnaire PedsQL for different age groups which has to be filled out by parents and/or patients

j For Electrocardiography (ECG), ophthalmological review and Echocardiography (Echo) please see Chapter 5. If a routine ophthalmological examination was done within 3 month before Visit 1, no additional ophthalmological exam is required.

k Pregnancy test only has to be performed in girls of childbearing age and only if sexual relations are known or probable. It is at the discretion and responsibility of the attending physician to decide, whether a pregnancy test is necessary or not. The pregnancy test can be performed in the urine or serum.

l The following parameter will also be assessed, if there is **oxygen demand**:

1. O2 via nasal cannula or via face mask: O2-Flow (l/min)
2. on high-flow nasal cannula: Flow air (l/min), O2-Flow (l/min), FiO2

m The following parameter will also be assessed on ventilation: ventilation method, duration of ventilation (hours/day/only for non-invasive ventilation), PEEP (cmH2O), PIP (cmH2O), FiO2, Ti (sec), MPAW (cmH2O) and Oxygenation Index (OI);  
In addition, if patients on the heart lung machine (e.g. NO (%), ECLS (VV/VA/ECLA), Flow/time since insertion) will be documented descriptively.

n Calculation of Oxygenation Index (OI): OI = (FiO2 \* MPAW)/PaO2

with MPAW = ((frequency \* inspiration time)/60) \* ((inspiratory pressure (PIP) – PEEP) + PEEP)); If PaO2 is not available, PcapO2 can be used.)

o Start date, End date, Patient returned to baseline function? Y/N

1. Increase in respiratory rate? Y/N/not done.

2. Increase or development of dyspnea ? Y/N

3. Newly developing or increased abnormalities on chest imaging ? Y/N/not done

4. Onset/increase of oxygen demand to attain the individual baseline saturation ? Y/N

5. Need for an additional level of ventilatory support (in addition to oxygen) ? Y/N

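### The schedule marks room-air saturation at the at-home contacts, and the linked oxygen-withdrawal step has no exemption for home

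*Protocol*

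**What the plan says.** Table 1-1 (START) has e-mail/phone contacts on days 7, 14, 21, 35, 42 and 49, described as "Every 7 days at home". Table 1-2 (STOP) has them on days 14, 42, 70, 98, 126 and 154; the first is headed "2 weeks of withdrawal, at home". In both tables the room-air saturation row, which carries footnote e, and the row "Respiratory rate, in room air" have an X in every one of these columns.

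Footnote e covers saturation, respiratory rate and oxygen flow. For a patient on oxygen it asks for a reading on oxygen first. Oxygen is then withdrawn until saturation in air is steady ("at least 30 seconds without change). Then measure twice over 1 min. each; the measurements have to be at least 1 min. apart"). If saturation falls below 80%, the instruction is to "place back in oxygen and note as exact value". Protocol Table 3.3-1 repeats the procedure. Neither place says where it is done or who supervises it.

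The SAP schedules (section 1.2) show a dash for saturation in the home columns and an X for room-air respiratory rate. SAP 4.2.1 agrees: saturation is excluded from web/tele feedback, while room-air respiratory rate is assessed at each one.

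**The concern.** A site or caregiver who follows the table and its footnote as written would take an oxygen-dependent child off oxygen at home. Entry is allowed from 3 weeks of age (Protocol 3.6.1), and Protocol 8.3.1 expects most children to be on supplemental oxygen or in room air. The 80% stopping rule needs someone watching an oximeter, but the text supplied describes no home device, caregiver instruction or supervision. Protocol 1.4 refers in general to close monitoring by physicians, and says that apart from a blood sample for drug level no test goes beyond ordinary care. It does not mention the home contacts.

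There is a smaller data problem. If sites do not withdraw oxygen at home, respiratory rates taken on oxygen may be filed under a room-air label and reach the descriptive tables that way.

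**Working it through.** The plan gives no figure to reproduce, so the check is a count of marks and a comparison of sections.

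**Marks and comparison days**

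| | START | STOP |
|---|---|---|
| Clinic visits with a room-air mark | 4 | 8 |
| Home contacts with a room-air mark | 3 + 3 = 6 | 3 + 3 = 6 |
| All marked occasions | 4 + 6 = 10 | 8 + 6 = 14 |
| Days compared between groups (SAP 6.6, 6.7.1) | 1, 28, 56 | 1, 84 |
| Home contacts among those days | 0 of 6 | 0 of 6 |

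Limiting withdrawal to clinic visits lowers the most withdrawals a child on oxygen could have from 10 to 4 in START and from 14 to 8 in STOP. No compared day is lost.

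**What the SAP covers.** Its START schedule has weekly home feedback in both treatment periods, with no saturation and with respiratory rate. Its STOP schedule lists only days 14, 42 and 70; days 98, 126 and 154 do not appear. The difference on saturation is therefore shown for all START home contacts but for only 3 of the 6 in STOP.

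**What an X in a home column can mean.**
- The Oxygenation Index row is marked in every home column. Footnote n needs an arterial or capillary oxygen pressure to calculate it, yet the blood-gas row is blank in those columns.
- The row "NO (%), ECLS (VV/VA/ECLA/Flow/time since insertion" is marked there too, although it describes intensive support.
- Physical examination, vital signs, ECG and walk test are blank, so the tables do distinguish between procedures.
- Oxygen demand has its own mark at each home contact, so support status is already captured separately.

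The first two items suggest that an X may mean only that information is collected. The last two mean that this reading cannot simply be assumed for the saturation row.

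**Is a room-air value needed at home?** Exacerbation is recorded at the same contacts. Its criteria in footnote o include "Increase in respiratory rate? Y/N/not done" and a rise in oxygen demand. Neither requires a room-air reading.

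**The case against.** The strongest reply is that the schedule does not mean what the literal reading says. An index that needs a blood gas cannot be newly obtained by phone when no gas is scheduled, so the X marks in these columns cannot all mean that the footnoted procedure is carried out. Footnote e's advice to "try to schedule patients at similar time of the day" reads like a clinic instruction. SAP 4.1 provides fields for saturation on oxygen, and lists the air challenge as a separate item with entries for not done and not tolerated. No text tells caregivers to remove oxygen, and the respiratory-rate row carries no footnote marker, although footnote e names that measurement. The SAP schedules also differ from the protocol in many other ways, such as six STOP visits against eight, so the dash for saturation may be general drift and not a decision.

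Most of this stands, and it makes home withdrawal less likely to be intended. It does not supply the missing exemption. With up to 100 sites planned (Protocol 3.2), an unwritten exception may not be read the same way everywhere. Consent pages are absent from the text reviewed and the EDC manual was not supplied, so the silence is established only for the protocol and SAP as available.

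**Conclusion.** The point holds as an unresolved instruction with a safety implication, and as a partial mismatch between protocol and SAP. Its weight is minor to moderate. It concerns six home contacts per block and only children on supplemental oxygen; their share is not stated, so no total is projected. Time off oxygen per block is not estimated either: the time to reach steady state is not given, and a fall below 80% would end the test early.

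A reader might infer three stronger things that the documents do not support.
- That children were, or were meant to be, taken off oxygen at home. Nothing shows this, and the Oxygenation Index and NO/ECLS marks point the other way.
- That the efficacy comparison is compromised. It uses clinic days only.
- That the SAP deliberately removed home saturation throughout. Half of the STOP home contacts are missing from its schedule.

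**What to change.** - In Tables 1-1 and 1-2 and footnote e, state that oxygen withdrawal is done only at clinic visits.
- Remove the room-air saturation mark from the e-mail/phone columns. This matches the SAP at the contacts it lists.
- At those contacts, record respiratory rate and oxygen demand on the child's usual support.
- In SAP 4.2.1 and both SAP schedules, drop the room-air label for home respiratory rate.

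The cost is wording in two protocol tables, one footnote, one SAP line and two SAP schedule rows. No planned comparison is lost. Children on oxygen would have no room-air home values, and their home respiratory rates would not be comparable with room-air clinic values. Home saturation would also no longer be collected from children breathing room air, as the SAP already has it for the contacts it lists.

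SAP 6.6 says in the past tense that patients in both blocks were too few, so conduct may be over. If it is, one sentence in the report should say whether home values were taken in room air or on support.
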